### Additional objectives due to the impact of COVID-19 at the study sites:

1. Develop data driven prediction models for identifying vulnerable children with suspected sepsis that are robust during future COVID-19 surges and novel pandemics.

- 2. Identify the variables that contribute to vulnerability in children with suspected sepsis, during pandemic and non-pandemic times.
- 3. Collect additional COVID-19 related prediction variables to inform understanding of the severity, risk factors, and clinical features of this disease at our three study sites (rural, urban and peri-urban).

**Objective B:** To validate the use of an automated Radio-Frequency Identification (RFID) method to track timeliness of interventions.

RFID tags will be small paper or plastic objects that can be attached to clothing or worn as a bracelet, anklet, or necklace (as preferred by child's caregiver) that use Bluetooth frequency band. The tag sends signals which allows tracking exactly where a patient is at a given time for analysis. For example, if a patient wearing an RFID tag enters a room, a reader in the room will detect the signal and add a timestamp for when patient was in the room. The Bluetooth frequency is no different to that used by mobile phones and is not expected to interfere with other processes in the hospital.

**Objective C:** To conduct an economic evaluation to contextualize our results for informing budgetary decisions of scaling-up Smart Triage.

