### Participant Involvement in Phase I and Phase III

Potential participants will be recruited by study nurses while they are waiting in line to be seen by the hospital triage nurses. Participants can anticipate study procedures (including consent, clinical examination, and interview) to take between 35 to 50 minutes. The **study nurses** will conduct study procedures in the triage waiting area, while the participant is waiting in line to be seen by the **hospital triage nurses**. If it is the participant's turn to be seen by the hospital triage nurses, study procedures will stop and there will be no interference or delays in accessing standard care. Participants will also engage in a short (10 minutes) follow up call 7-days postdischarge.

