IF gestage_known = no			
gestage_est	Approximate gestational age in months (reported)	Ask: How many months (weeks) was the mom pregnant when the child was born?	0, < 7 (28) 1, 7-8 (28-32) 2, > 8 (32) 98, Don't know
IF age < 12 months			

facility_birth	Facility of birth (reported)	Ask: Where was the child born? Read out options.	1, Hospital 2, Health centre 3, Clinic 4, Home 5, Other 98, Don't know
Other			· · ·
parent_concern	Parental Concern	Ask: Do you think your child needs to be admitted to the hospital?	0, No 1, Yes 2, Healthcare workers should decide
COVID-19 QUESTIONS			
IF fever = YES or difficulty_breath_rep =	• YES or difficulty_breathing_ob	s = YES or temp >= 37.5	
covid_contact	Contact with a confirmed or suspected COVID-19 case	Ask: In the 14 days before getting sick, has the child been in contact with someone who tested positive for COVID-19 or someone suspected to have COVID-19?	0, No 1, Yes
IF covid_contact = YES			
covid_confirmed	Contact with a confirmed case	Ask: Was the contact with someone who tested positive for COVID-19?	0, No 1, Yes
contact_source	Source of contact	Ask: What is the relationship between the person of contact and the child?	1, Parent 2, Sibling 3, Grandparent 4, Extended family 5, Caregiver or nanny 6, Friend 99, Other
IF contact_source = OTHER	1		
source_other	Other source of contact	Please specify the relationship between the person of contact and the child.	
contact_setting	Setting in which the contact occurred	Ask: In what setting did the contact occur? (read options)	1, Child's home 2, Extended family's home 3, School/Daycare 4, Friend's house 5, Parent's workplace 99, Other
IF contact_setting = OTHER			
setting_other	Other setting in which the contact occurred	Please specify the setting in which the contact occurred.	
profession_risk	Family with a high-risk profession	Ask: Does the child have a parent or family member working in any of the following fields? (read out options)	1, Healthcare 2, Laboratory 3, Market 4, Driver/Public Transport 5, School teacher

Wellcome Trust

facility_risk	Facility Risk	Ask: Has the child visited any healthcare facility in the 14 days prior to symptom onset?	0, No 1, Yes
covid_test	COVID-19 test done?	Has the child been tested for COVID-19?	0, No 1, Yes
IF covid_test = YES			
covid_result	COVID-19 test result	Select COVID-19 test result.	0, Negative 1, Positive 2, Inconclusive 3, Results not yet available
Outcomes			
Hospital Outcomes	1	1	

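### Added COVID-19 objective 3 needs each child's final COVID-19 status, but the structured fields sit only in the enrolment part of the form, apparently behind a symptom gate, with no item for a later result

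*Combined protocol and SAP*

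**What the plan says.** Section 6 of the Version 5.0 protocol adds three objectives because of the pandemic. The third is to collect further COVID-19 variables to "inform understanding of the severity, risk factors, and clinical features of this disease at our three study sites".

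The variables are in the COVID-19 block of the Data Dictionary (Appendix A). The block opens with a condition that begins "IF fever = YES or difficulty_breath_rep" and ends "s = YES or temp >= 37.5". It therefore covers reported fever, reported or observed difficulty breathing, and raised temperature. Questions on contacts, family occupation and recent facility visits follow. The last two items are `covid_test`, prompted by "Has the child been tested for COVID-19", and `covid_result`, which offers negative, positive, inconclusive and, as its last option, "3, Results not yet available". The Outcomes heading comes next.

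Section 12 places the interview before hospital triage: "The study nurses will conduct study procedures in the triage waiting area".

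**The concern.** To describe how severe a disease is, what predicts it and how it presents, one must be able to classify each child as having it, not having it, or unknown. Three features of the form work against that.

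- If the opening condition covers the whole block, children who present otherwise, for example with vomiting or diarrhoea alone, have no recorded status. Fever or respiratory signs among recorded cases would then be partly a product of the form.
- The items belong to the enrolment part, and pending is an accepted answer, but no later item asks again.
- A case recognised later has no code of its own, so it can be found only through free text that some children never reach.

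At stake is the description of COVID-19 at the sites. No primary or secondary outcome in section 11 uses these fields.

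**Working it through.** The documents give no COVID-19 testing rate, prevalence, share of pending results or target number of cases, so no arithmetic applies. The check sets the objectives, the form and the analysis plan side by side.

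1. **Which objectives need child-level status.** Under the COVID-19 analyses in section 17, the work for objective 1 compares model performance in the pandemic and non-pandemic periods and validates on data from both. The work for objective 2 compares cohorts by period. Neither uses a child's test result. Objective 3 does, and section 17 gives no analysis for it. One of the three added objectives is affected.

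2. **Where status is recorded.** `covid_test` and `covid_result` are the only structured items. Neither has a date. The haemoglobin, glucose, lactate and bilirubin items each ask whether the test was done on the day; `covid_test` does not. A test from an earlier illness therefore cannot be told from one for this visit.

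3. **Who is asked.** The condition stands directly under the block heading, so the natural reading is that it governs the block. The dictionary does not define the reach of its IF rows, however. `contact_setting` comes after "IF contact_source = OTHER" and cannot sensibly depend on it. The gate is the likely reading, not a certain one. It matters in practice because section 16 says the app hides questions dynamically.

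4. **Whether a later item closes the gap.** Going through the remaining forms:
   - Hospital Outcomes: admission, diagnosis, dates, status if not admitted, and death on the enrolment day. One non-admission option is referral to a facility not handling COVID-19, which is not a test or a result.
   - Follow-up Call: death, readmission, care sought and lost wages. No COVID-19 test or result.
   - Clinical Timekeeper: treatment times and delays. No COVID-19 test or result.

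5. **Whether a diagnosis code substitutes.** Final diagnosis is asked only for admitted children. Its codes run from 1 to 12 plus 99, which makes 13 options, none of them COVID-19. The readmission-reason list has the same 13. A later diagnosis can therefore appear only as free text in `diagnosis_other` (admitted), `reason_other` (readmitted), or `deathcause_enrol` and `deathcause` (died). A child who was neither admitted, readmitted nor dead has no route. Cases identified late are thus tilted towards the severe end of what objective 3 is meant to describe.

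Points 2, 4 and 5 hold whether or not the gate applies to `covid_test`.

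**The case against.** The strongest reply is that much of the harm would have to be inferred, and in several places it is right.

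- **Time of completion.** A reader might infer that a test ordered at this visit is bound to be entered as not done, because the interview precedes the consultation. The documents do not support that. Malaria and blood results sit in the same part of the form, yet section 23 says such testing is communicated at the consultation after triage, so position does not fix when a field is filled. `covid_test` also lacks the instruction to ask the caregiver that the contact items carry, so completion from records is not excluded. In emergencies, study procedures start only after treatment has begun (section 21).
- **Pending results.** A reader might infer that they are never updated. The documents are silent: the original field may be editable, and section 18 provides for completeness reports. What can be said is that no update item or procedure is documented.
- **Modelling.** A reader might infer that the surge-robust prediction models suffer too. They do not, because they are built on period.
- **The gate.** It may not reach `covid_test`. If it does, any reported history of fever satisfies it, so it is broad, and the share of children outside it is not given.
- **Ambition.** Objective 3 is exploratory, with no estimand or target number, and exposure items and available results still serve it.

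These points narrow the concern but leave its core. No printed item takes a later test or final result, there is no date, and there is no COVID-19 code.

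**Conclusion.** The concern holds for added objective 3 only. As printed, that objective can be addressed only in a selected and incompletely ascertained subgroup. It would be too strong to say that it cannot be answered at all: exposure data, available results and free-text diagnoses still allow a limited description of tested children, mainly symptomatic ones if the gate applies.

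The size of the loss cannot be stated, and any count would only restate an assumption about how many children are tested and how many results are pending. Nor do the documents show that children tested after the interview are sicker than the rest. The selection by symptoms rests on the natural reading of the gate; the lack of a later capture point, a test date and a diagnosis code does not.

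The change is worth making because it improves the data for a stated objective at contacts that already take place. It does not bear on the primary outcomes.

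**What to change.** - Keep the contact and exposure questions at enrolment.
- Record COVID-19 test done, test date and final result on the Hospital Outcomes form, from records, for every child and without the symptom condition.
- Add one item to the 7-day call that captures tests done since the visit and replaces a pending result.
- Add a COVID-19 code to the final-diagnosis and readmission-reason lists.
- Write the missing analysis for objective 3: describe features on final status among tested children, show separately who was tested, and report untested children and results still pending as unknown, not as negative.

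Removing the gate does not make testing systematic. Which children are tested will still shape the picture, which is why it must be reported alongside the results.

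The cost is a small amount of extra data entry at the existing record abstraction and call, with no added testing or visits. Records already collected under the old coding must be flagged, and some of their final results may not be recoverable.

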confirm_admission	Confirm Date of Admission	Ask: What date was your child admitted to the hospital? (See SOP).	
confirm_discharge	Confirm Date of Discharge	Ask: What date was your child discharged from the hospital? (See SOP).	

*readmitted	7-day	Ask: Was the child admitted to	0. No
readmitted	Readmission/admissio	any hospital after being	1, Yes
	n to another hospital	discharged? (See SOP).	
	after discharge		
IF readmitted = yes			
readmitted_reason	Reason for readmission/admissio n to hospital after discharge	Ask: What was the reason the child was admitted?	1, Malaria 2, Pneumonia 3, Bronchiolitis 4, URTI (cold, flu, etc) 5, Reactive airway disease/asthma 6, Gastroenteritis/Diarr hoea 7, HIV/AIDS or AIDS related illness 8, Meningitis/encephalit is or other CNS infection 9, Malnutrition 10, Tuberculosis 11, Any skin or soft tissue infection
			12, Measles
*readmitted location	Location of	Ask: Which hospital was the	99, Uther
	readmission/admissio	child admitted to?	
	n to hospital after		
IF wood without woodow - other	discharge		
IF readmitted_reason = other			1
reason_other	Readmission Reason Other	If reason for readmission is 'other', please specify,	
readmitted_tx	Treatment Received During Readmission	What treatment was the child given when readmitted?	0, None 1, Antibiotics 2, Intravenous Fluids 3, Oxygen 99, Other
IF readmitted_tx = other			
readmitted_tx_other	Treatment Received During Readmission Other	If treatment is 'other', please specify.	
*readmitted_date_known	Readmission dates known	Do you know exactly what dates the child was admitted again and discharged again from the hospital?	0, No 1, Yes
IF readmitted_date_known = y	es		
*readmitted_start	Readmission date	What date was the child admitted again from the hospital after being sent home?	
*readmitted_end	Readmission discharge date	What date was the child sent home again after being readmitted?	

*readmitted_los_calc	Length of stay on readmission	Calculated length of stay on readmission	
IF readmitted date known =	(calculated)		
*readmitted_los_reported	Length of stay on readmission (reported)	When your child was admitted to the hospital again, how many days did your child stay in hospital?	
IF readmitted = yes			
*seek_help_before_readmit	Seeking help at medical facility before readmission	Ask: Other than the place where your child was readmitted, did you seek any other medical help?	0, No 1, Yes
IF readmitted = no			
*seek_help	Seeking help at medical facility (regardless of readmission)	Ask: Did you seek help from a medical facility after being discharged from hospital?	0, No 1, Yes
IF readmitted = yes OR seek_h	nelp = yes	e	
(invoke branching logic to find	out what the care center o	f readmission/seeking help was)	Text field populated
*center_district	District of care center	Ask: In what district was the care center where the child was readmitted/sought help?	by app. 13 choices
*center_sub_district	Health Sub District of care center	Ask: In what sub-district was the care center where the child was readmitted/sought help?	Text field populated by app, choices depends on answer to readmitted district.
*center_name	Health Facility of care center	Ask: What was the name of care center where the child was readmitted/sought help?	Text field populated by app. Choices depends on answer to readmitted_sub_distr ict
*center_tier	Care center tier of health facility.		Auto-populated by app depending on answer to center_name
*center_own	Ownership of health facility		Auto-populated by app depending on answer to center_name
			Govt vs. PNFP vs. PFP (government, private not for profit, private for profit)
IF ask_missed_wages = 1 OR r (note: will ask about missed we everyone else). Included read	eadmitted = yes or seek_h ages if patient was readmit mitted or seeking help to ge	elp = yes ted, sought help after discharge, or i et a representative sample size in th	20% of the time for ese grouops as N is
*who missed wages	Person who missed	Ask: During this illness who	1 Mother
who_missed_wages	wages, to calculate indirect costs of illness	missed daily wages as a result of the child being sick [read out	2, Father 3, Other relative

Wellcome Trust

		options and check all that apply]?	98, Other 99, Don't know
IF who_missed_wages = Mo	ther	1 - mm (74)	
*days_missed_wages1	# days missed wage mother	Ask: During this illness, how many days of paid work did the mother miss?	Number, min:0, max: 10
IF who_missed_wages = Fat	her		
*days_missed_wages2	# days missed wage father	Ask: During this illness, how many days of paid work did the father miss?	Number, min:0, max: 10
IF who_missed_wages = Rel	ative		
*days_missed_wages3	# days missed wage relative	Ask: During this illness, how many days of paid work did the relative miss?	Number, min:0, max: 10
IF who_missed_wages = Oth	ner		
*days_missed_wages98	# days missed wage other	Ask: During this illness, how many days of paid work did this individual miss?	Number, min:0, max: 10
Clinical Timekeeper	· · ·		
study_id	Study ID	Enter the study ID recorded in the participant's notebook.	
study_id_2	Study ID	Again, enter the study ID recorded in the participant's notebook.	
*abx_time	Time at start of antibiotics administration.	Time at start of antibiotics administration.	
*fluids_time	Time at start of intravenous fluids administration.	Time at start of intravenous fluids administration.	
*oxygen_time	Time at start of oxygen administration.	Time at start of oxygen administration.	
*antimalarial time	Time at the start of antimalarial administration.	Time at start of antimalarial administration.	
other_time	Time at start of treatments that are NOT antibiotics, fluids or oxygen.	Time at start of treatments that are NOT antibiotics, fluids or oxygen.	
IF tx = other			
tx_other	Treatment Received Other	If treatment is 'other', please specify.	
tx_delay	Patient received all treatments on time.	Patient received all treatments on time (choose No if a treatment was not received on time)	0, No 1, Yes
in the utility - i to			

delay_reason	Reason for receiving delayed treatment	Why didn't the patient receive treatment on time?	1, Out of stock 2, All health workers were busy (no one available to treat)
--------------	--	---	--

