#### **Economic Evaluation**

We will conduct a cost-effectiveness analysis of Smart Triage by calculating the cost per averted year of life lost (YLL) using decision analysis. Previous models (21) and expert opinion has been consulted for potential pathways of healthcare utilization. We will model uncertainty using probabilistic sensitivity analysis and will take a societal perspective as our base case.

Probabilities of healthcare utilization will be calculated via primary data from the Smart Triage case report form. The primary outcome of "time to bundle of care" will be linked to mortality via existing evidence (22) as required in order to calculate YLL, as Smart Triage was not originally powered to detect mortality. We will use the World Health Organization's life expectancy data in Uganda (23) to calculate projected YLL before and after program implementation. Costs of healthcare utilization is available through existing literature (21, 24), and indirect costs due to lost wages will be gathered as primary data in Smart Triage. Costs of program setup and maintenance will be tracked from study expenses and incorporated into the analysis.

To contextualize our results for informing budgetary decisions of scaling-up Smart Triage, we will estimate a projected budget impact of scale up given the disease burden of pediatric sepsis in Uganda (25), as recommended for newly proposed healthcare programs (26). The results of this preliminary budget impact analysis can be refined in further multicenter trials and can be compared to that of other programs to facilitate healthcare resource allocation in Uganda.

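### Missed paid work is limited to 10 days per earner, but the period asked about can be longer for admitted or readmitted children, so indirect costs can be understated in the costliest pathways

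*Combined protocol and SAP*

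**What the plan says.** Appendix A (Data Dictionary, Follow-up Call) first asks who missed wages because of the child's illness. It then opens a day count for each person named: mother, father, relative or other. Each count has the same definition, "Number, min:0, max: 10". The wording for the mother is "During this illness, how many days of paid work did the mother miss", and the other three are parallel. The question is thus tied to the illness, not to a fixed number of days.

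Section 12 gives the timing of the call: "Participants will also engage in a short (10 minutes) follow up call 7-days postdischarge".

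Section 17 (Economic Evaluation) takes a societal base case and states that "indirect costs due to lost wages will be gathered as primary data in Smart Triage". Costs of care come from the literature and programme costs from study expenses, so lost wages are the only household cost that the study collects itself. The model is a decision analysis over pathways of healthcare use, with pathway probabilities taken from the case report form. The section does not mention the 10-day limit or how values at the limit are to be handled.

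A note above the wage questions, damaged in the text available, indicates that families whose child was readmitted or who sought further help are always asked, and that the rest are asked "20% of the time for" everyone else.

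**The concern.** The question and its answer field do not match. The question runs over the whole illness up to the call; the field stops at 10 days per person. Where a parent truly lost more, the excess is never recorded and no later analysis can restore it.

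The error can only go one way, downward, and it falls on children with a long illness, a long stay or a readmission. Those pathways carry the most indirect cost. They are also where a saving from earlier treatment could appear: if lost days fall from one value above 10 to a smaller value still above 10, both are recorded as 10 and the saving is invisible. At stake is one cost input to Objective C, not the primary or secondary outcomes.

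**Working it through.** The plan states no figure for missed days or indirect cost, so there is nothing to reproduce. The check is whether the period asked about can hold more than 10 working days.

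**Inputs**
- Limit: 10 days per earner (Appendix A, Follow-up Call).
- Time from discharge to the call: 7 days (Section 12).
- *d*, days ill before arrival, and *s*, length of stay: both are recorded for the study (Appendix A), but no values are given.
- *r*, readmission days that fall outside the 7 days already counted. The documents do not say whether the call is moved after a readmission, so *r* is set to 0 below.
- *k*, working days per week: an assumption, either 5 or 7.

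**Step 1. Most working days one earner could lose**

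W = d + s + 7 + r calendar days, and M = W × k/7 working days.

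**Step 2. When M exceeds 10 (r = 0)**
- k = 5: W > 10 × 7/5 = 14, so d + s > 7.
- k = 7: W > 10, so d + s > 3.

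**Step 3. Two examples, both with an assumed d = 3**

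| Child | W | M, 5-day week | M, daily work |
|---|---|---|---|
| Admitted, assumed s = 10 | 3 + 10 + 7 = 20 | 20 × 5/7 = 14.3 | 20 |
| Not admitted, s = 0 | 3 + 0 + 7 = 10 | 10 × 5/7 = 7.1 | 10 |

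For the admitted child, up to 14.3 − 10 = 4.3 days (5-day week) or 20 − 10 = 10 days (daily work) could not be recorded. For the child who is not admitted, the limit is not exceeded in either case. M is a ceiling: it is reached only if the earner misses every working day from onset to the call.

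**Step 4. Size**

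The understatement depends on how many earners lose more than 10 days and by how much. The documents give neither. Simulation with assumed gamma-distributed days (mean 2 to 7, coefficient of variation 0.7 to 1.5) lowered the mean by anything from 0% (mean 2, smallest spread) to 39% (mean 7, largest spread). So wide a range shows only that the answer is set by the assumption. It is not evidence of the size in this study.

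**Step 5. The 20% subsample**

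Let *q* be the share of families always asked, with mean m₁, and let m₀ be the mean in the rest.
- Per-pathway estimate: q·m₁ + (1 − q)·m₀.
- Weighted estimate, weights 1 and 1/0.2 = 5: [q·m₁ + (1 − q)·0.2·5·m₀] / [q + (1 − q)·0.2·5] = q·m₁ + (1 − q)·m₀.

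The two agree and equal the population mean. Neither repairs the cap.

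**The case against.** The strongest case against is that the limit will seldom matter. Section 13 plans on an admission rate of 12%, and Step 3 shows that a child who is not admitted after 3 days of illness stays within the limit. The admitted example needs an assumed 10-day stay and a parent who loses every working day, including the week after discharge. The limit is per person over four fields, so a household can record up to 4 × 10 = 40 days. The documents also do not say whether the maximum blocks entry or only prompts a check. All of this stands as a reason not to put a size on the error. It does not remove the mismatch: one earner's days above 10 do not belong in another person's field, and no soft-warning rule is described.

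A second objection is that recruitment at Jinja has already begun (Section 8). Lifting the limit now could leave baseline capped and the intervention phase not, which would distort the pre-post cost comparison. That is correct, and the fix has to deal with it.

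A reader might also infer three stronger points, which the documents do not support.
- *That the unequal sampling biases indirect costs.* Section 17 nowhere says that wage answers will be pooled unweighted. It plans a model over utilization pathways, and readmission and help-seeking look like natural branches of it. By Step 5, branch means multiplied by branch probabilities carry no sampling bias. What is missing is a sentence, not a valid method.
- *That the cap and the sampling produce errors that fail to cancel.* The cap can act only downward. Unweighted pooling, if it were done and if the oversampled families lost more days, would act upward. The net sign is not determined.
- *That there is no code for a family in which nobody lost wages.* The option list is split across a page in the available text, so absence of a code cannot be concluded. The item allows several answers, has a separate don't-know code, and the families asked can be identified from other fields.

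**Conclusion.** The point holds for the cap. If the maximum works as an entry limit, Appendix A can cut off true lost days for admitted or readmitted children, and indirect costs in the societal base case can then be understated in the costliest pathways. The direction is certain where the limit binds. The amount cannot be estimated, because the documents give no length of stay, no days ill before arrival and no distribution of missed work. The thresholds in Step 2 rest on the assumed working week and on the illness, as the family understands it, lasting until the call.

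The change is worth making because values lost at the call cannot be recovered, whereas the treatment of the subsample can still be settled at analysis.

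**What to change.** 1. In Appendix A, replace the maximum of 10 in all four day-count fields with a higher fixed limit that covers the longest plausible period from onset to call. Keep 10 only as a soft warning that asks the interviewer to confirm. A fixed limit avoids a check across forms, which would fail where readmission dates are unknown.
2. Flag every value of 10 already recorded as possibly censored.
3. In Section 17, add a sensitivity analysis that repeats the pre-post cost comparison with the 10-day cap applied to both phases. This keeps the phases comparable if the limit changes mid-study.
4. As a clarification only, state in Section 17 that wage loss is estimated per decision-tree pathway, or with weights of 1 for families always asked and 5 for the 20% sample.

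The cost is an app setting, a data flag, one extra analysis and two or three sentences of text. The downside is small: data already collected stay censored at 10, and the common-cap analysis compares the phases only on the first 10 days per earner.
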